12.4 Analysis Sets

12.4.1 Safety Analysis Set

The SAF consists of all enrolled subjects who have received at least 1 dose of investigational product.

12.4.2 PK Set

The PK population is defined as all subjects who have received the investigational product, did not have major protocol deviations or other events that may affect PK, and have sufficient plasma concentration. The PK population will be finalised prior to database lock.

12.5 Background and Demographic Characteristics

The number of subjects enrolled, treated, completed, or discontinued from the study, along with the reason for discontinuation, will be summarised.

In addition, the number of subjects in each analysis set will be tabulated.

Subject demographics and baseline characteristics will be summarised using descriptive statistics on the SAF; no formal statistical analysis tests will be performed.

For quantitative variables the mean, SD, median, minimum and maximum will be calculated. For qualitative variables, frequencies and associated percentages will be tabulated.

Medical history data will be coded using MedDRA and summarised by MedDRA SOC and PT. The data will also be listed, including the verbatim Investigator description of the relevant medical condition, the coded terms (SOC, PT), start date, end date, and whether or not the condition is ongoing.

12.6 Investigational Product

The investigational product will be administered as a single dose of $0.5~\mu g/kg$, 3 times a week over a period of one week. The total amount of investigational product given will be calculated for each subject and will be compared to the amount expected to be given for each subject. Treatment compliance will be calculated for each subject and summarised overall.

In addition, the number and percentage of subjects who were administered 1, 2, or 3 doses will be summarised with the actual dose received at each administration, i.e., on Day 1, 3, and 5.

Results will be summarised on the SAF by means of descriptive statistics (n, mean, SD, median, minimum, quartiles and maximum) for quantitative variables and by means of frequencies and associated percentages for qualitative variables.

12.7 Concomitant Therapy

Medications will be coded using the World Health Organization Drug Dictionary. Counts and percentages of subject use for each concomitant medication will be tabulated by appropriate World Health Organization Drug Dictionary classifications on the SAF. Prior medications will be presented in a listing only using the SAF. Traditional Chinese medicines should also be recorded.

A prior medication is defined as any medication taken any time with an end date before the date of the first administration of investigational product.

A concomitant medication is defined as any medication/therapy used on or after the date of the first administration of investigational product or with a missing end date. If missing, the medication will be assumed to be ongoing and considered as concomitant.

12.8 Pharmacokinetics

All PK analyses will be performed using the PK analysis set.

Noncompartmental PK analysis will be applied to derive all PK parameters in this study.

Plasma difelikefalin concentrations will be summarised descriptively by nominal time at each time point. Individual and mean plasma concentration-time profiles and spaghetti plots (individual subject profiles in one plot) will be provided. In addition, individual plasma difelikefalin concentrations will be listed by subjects.

All PK parameters (e.g., C_{max}, T_{max}, AUC_{0-t}, AUC_{inf}, AUC_{Extrap(%)}, t½, clearance, and V_z) will be summarised descriptively. Descriptive statistics will include N, mean (arithmetic and geometric), SD, median, coefficient of variation, minimum, quartiles, and maximum.

12.9 Efficacy Evaluations

Not applicable.

12.10 Safety Evaluations

All safety analyses will be performed on the SAF. Incidence of AEs, AESIs, and SAEs will be tabulated by SOC and PT, using MedDRA coded terms. Incidence of AEs will also be summarised by maximum intensity and maximum relationship to the investigational product. Vital signs, biochemistry, haematology data, and 12-lead ECG recordings will be descriptively summarised by visit as applicable, in addition to change from baseline. Details are listed as below.

12.10.1 Adverse Events

All AEs and pre-treatment AEs will be coded using MedDRA to MedDRA SOC and PT for standardisation and summary purposes.

All reported AEs will be included in summary tables and in by-subject AE listings.

An AE is defined as any AE that has an onset on or after the first investigational product administration, or any pre-existing condition that has worsened on or after the first administration of investigational product.

A pre-treatment AE is defined as any AE that has an onset before the first investigational product administration.

The number and percentage of subjects experiencing AEs, as well as the number of events will be summarised. A subject will be counted only once in the incidence count for a MedDRA SOC or PT, although a subject may have multiple occurrences (start and stop) of an event associated with a specific MedDRA SOC or PT.

In addition, the incidence and percentage of subjects experiencing treatment-emergent SAEs and AEs leading to investigational product discontinuation will be presented by the appropriate MedDRA SOC and PT.

AEs will also be summarised by severity and by relationship to investigational product. If the severity and/or relationship to the investigational product of an AE is missing, a worst-case scenario will be assumed (i.e., the AE will be categorised as "severe" and/or

"related" to the investigational product). If a subject reports the same AE multiple times the event with the worst severity and the strongest relationship to investigational product will be tabulated.

An overall summary table will be provided, presenting the number and percentage of subjects as well as the number of events for AEs, SAEs, treatment-emergent deaths, treatment-related AEs, treatment-related SAEs, severe AEs, AEs leading to investigational product discontinuation and AESIs.

In addition, the following summary tables will be presented and will include the number and percentage of subjects as well as the number of events for:

- AEs by SOC and PT
- SAEs by SOC and PT
- AEs by SOC, PT, and maximum severity
- Related AEs by SOC and PT
- AEs leading to investigational product discontinuation by SOC and PT
- AESIs by PT
- Related AESIs by PT

All AEs will be listed in chronological order, including information such as subject identifier, age, sex, a flag indicating whether the event was treatment-emergent, and all related event status information (start and stop dates, whether the event was ongoing, study day of onset, severity, seriousness, relationship to investigational product, action taken with investigational product, and outcome). Separate listings will be generated for SAEs, deaths, AEs leading to investigational product discontinuation, and pre-treatment AEs. Pre-treatment AEs will not be included in any summary tables.

12.10.2 Special Situations

All special situations will be coded using MedDRA (when applicable).

All reported special situations will be included in a by-subject listing.

12.10.3 Vital Signs

Summary statistics for absolute vital sign value and the changes from baseline will be presented for each visit.

12.10.4 12-lead ECG

Baseline and change from baseline in ECG parameters will be summarised at each post-baseline time point.

All 12-lead ECG data will be listed in a by-subject listing.

12.10.5 Physical Examination

Not applicable as physical examination findings will be recorded through medical history or AEs if clinically relevant.

12.10.6 Clinical Laboratory Tests

Summary statistics for absolute value and the changes from baseline will be presented for each visit and for each laboratory variable. In addition, each reading will be classified as below, within, or above normal range, based on ranges supplied by the laboratory used. Shift tables from baseline to each post-baseline time point measurements will also be presented.

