4. INVESTIGATIONAL PLAN

4.1 Overall Study Design

This is a Phase 1, single-arm, uncontrolled, open-label study to evaluate the PK, safety, and tolerability of a repeated (3 times weekly) dose of difelikefalin administered as IV bolus injections to adult Chinese HD subjects (Figure 1).

Subjects eligible for the study will receive a unique subject number. Enrolled subjects who terminate their study participation for any reason regardless of whether the investigational product was administered or not, will retain their number. The next subject will be given the next unique subject number.

Enrolled subjects will be administered 0.5 μ g/kg of difelikefalin as a single IV bolus 3 times, within 15 minutes post-dialysis for 1 week. The first dose will be administered on Day 1. The first HD will be the first scheduled dialysis day of the calendar week for the subject (i.e., Monday, or Tuesday).

The schedule of assessments is provided in Table 1.

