5.2 Inclusion Criteria

Subjects are eligible to be included in the study only if all of the following inclusion criteria apply:

- 1. Appropriate written informed consent has been provided by subject or legally acceptable representative. Written informed consent must be provided before any study-specific procedures are performed, including screening procedures.
- 2. Subjects have the ability to understand the requirements of the study, in the Investigator's opinion.
- 3. Chinese subjects aged ≥ 18 to 85 years (inclusive), at the time of consent.
- 4. End-stage renal disease (ESRD) subjects who have been on HD for at least 3 months before enrolment in the study and are currently on HD 3 times per week. Subjects with or without associated pruritus may be enrolled.
- 5. Subjects with a prescription dry body weight between 40 and 100 kg, inclusive.
- 6. If female, is not pregnant, or nursing.
- 7. If female:
 - a. Is surgically sterile; or
 - b. Has been amenorrhoeic for at least 1 year and is over the age of 55 years; or
 - c. Has a negative serum pregnancy test within 7 days before first dose of investigational product, and agrees to use adequate contraceptive precautions (e.g., hormonal contraceptives, barrier with spermicide, intrauterine device, vasectomised partner, or abstinence) from the time of informed consent until 7 days after the last dose of investigational product. Note: If the result from serum pregnancy testing at screening is indeterminate due to possible human chorionic gonadotropin elevation secondary to ESRD unrelated to pregnancy, a serum pregnancy re-test may be repeated prior to treatment Day 1 to establish if a negative result can be confirmed.

8. If male, agrees not to donate sperm from the first dose of investigational product administration (Day 1) until 7 days after last dosing, and agrees to use a condom with spermicide or abstain from heterosexual intercourse during the study until 7 days after the last dose of investigational product. Note: No restrictions are required for a vasectomised male, provided his vasectomy was performed ≥4 months prior to screening.

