9.2 Physical Examination, Height, Vital Signs

Physical examination will include general appearance, cardiovascular, respiratory, abdominal, musculoskeletal, neurological, lymph nodes, and skin. Any findings before first administration of investigational product should be reported in the medical history. Clinically significant findings after first administration of study drug should be reported as AEs.

Height without shoes will be recorded in centimetres.

Vital signs will include body temperature (°C), respiratory rate, radial pulse rate, systolic and diastolic blood pressures. Sitting recordings are to be made after the subject has been sitting for at least 5 minutes with their feet squarely on the floor and arms relaxed, bent at the elbow.

An AE form must be completed for all changes identified as clinically noteworthy.

9.3 12-lead ECG

Standard 12-lead ECGs will be measured after the subject has been resting for minimum of 5 minutes.

All 12-lead ECG recordings (including heart rate, QT, QTcF, QTcB, RR interval, P-wave, QRS complex duration, and PR interval) will be performed and interpreted at study sites by Investigators. ECGs will be planned to coincide with first dialysis of the week. If this is not possible, ECGs should be planned for the same session of the week.

At screening, the Investigator must document clinically relevant ECG findings on the appropriate baseline eCRF pages. Any new clinically relevant ECG finding, or aggravation/worsening of an already existing finding as assessed by the Investigator, must be reported as an AE (see Section 10).

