9.7 Dialysis

The HD prescription should be kept constant throughout the study. If the dialysis prescription must be changed or if there is an access problem that precludes achieving the prescribed blood flows, please contact the Medical Monitor. Record procedural data (start and stop times, net ultrafiltration, access changes).

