12.11 Other Evaluations

12.11.1 Dialysis Details

Dialysis details will be listed only using the SAF.

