12.12 Handling of Missing Data

Procedures for managing missing data, imputation for missing or partially missing data will be provided in the SAP.

Definitions of baseline will be specified in the SAP and will include rules for identification of baseline values when assessments are missing at the scheduled baseline visit.

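### Do the Day 3 and Day 5 laboratory and vital-sign changes need a session-matching rule because they follow a shorter dialysis gap than Day 1?

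*Combined protocol and SAP*

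**What the plan says.** Section 5.2 admits subjects who "are currently on HD 3 times per week". The Synopsis makes Day 1 the first dialysis session of the subject's week and schedules dialysis on Days 1, 3, 5, 8, 10 and 12. Table 1 takes chemistry, haematology and vital signs within two hours before dialysis on Days 1, 3, 5 and 8, and again at end of study.

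On analysis, Section 12.10.3 states: "Summary statistics for absolute vital sign value and the changes from baseline will be presented for each visit". Section 12.10.6 does the same for each laboratory variable, and "Shift tables from baseline to each post-baseline time point measurements will also be presented". Neither section mentions the time since the previous dialysis. Section 12.12 leaves the reference point open: "Definitions of baseline will be specified in the SAP". Section 12.1 describes its own content as general and sends detailed methods to the SAP, which is not among the documents available here. Section 12.11.1 says "Dialysis details will be listed only using the SAF".

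Section 9.3 does have a session rule, for ECGs only: "ECGs will be planned to coincide with first dialysis of the week", or failing that the same session of the week.

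**The concern.** Dialysis three times a week leaves one long and two short gaps. A substance that dialysis clears well and that builds up between sessions peaks before the first session of the week. If Day 1 is baseline, Days 3 and 5 are compared with that peak, so they would tend to read lower with no drug effect.

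Section 4.1 says "This is a Phase 1, single-arm, uncontrolled, open-label study", so no comparator arm shows how much of a change is timing. A downward drift could hide part of a real rise. Potassium is in the panel, and Section 1.2.2.2 lists hyperkalaemia among the common events that exceeded placebo in haemodialysis subjects. In the shift tables, a value above range on Day 1 could move to within range on Day 3 or 5 for reasons unrelated to treatment. Since the protocol matches ECGs by session, the lack of a similar rule for laboratory values and vital signs looks like an oversight.

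**Working it through.** **Gaps.** Days since the previous scheduled session, counted from the calendar, are the same on the Monday-Wednesday-Friday and Tuesday-Thursday-Saturday schedules:

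| Visit | Gap (days) | Versus Day 1 |
|---|---|---|
| Day 1 | 3 | reference |
| Day 3 | 2 | unmatched |
| Day 5 | 2 | unmatched |
| Day 8 | 3 | matched |
| Day 15 | 3 | matched |
| Day 17 | 2 | unmatched |

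The end-of-study visit is Day 14 plus up to 3 days and must fall on a dialysis day. Days 14 and 16 are not dialysis days on either schedule, which leaves Day 15 or Day 17.

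**Size under an assumed model.** The plan gives no figure to reproduce and no removal fractions. Assume constant build-up, a fixed fraction f removed per session (consistent with Section 9.7: "The HD prescription should be kept constant throughout the study") and no drug effect. Let r = 1 − f. In a steady weekly cycle with gaps of 3, 2 and 2 days, the pre-dialysis levels are:

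- Day 1: M = (3 + 2r + 2r²)/(1 − r³)
- Day 3: W = rM + 2
- Day 5: F = rW + 2
- Day 8: rF + 3, which equals M

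For f = 0.5: M = (3 + 1 + 0.5)/0.875 = 5.143, W = 4.571, F = 4.286. Hence W/M − 1 = −11.1% and F/M − 1 = −16.7%.

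| Removed per session | Day 3 vs Day 1 | Day 5 vs Day 1 | Day 8 vs Day 1 |
|---|---|---|---|
| 10% | −1.6% | −3.0% | 0% |
| 30% | −5.6% | −9.5% | 0% |
| 50% | −11.1% | −16.7% | 0% |
| 70% | −18.5% | −24.1% | 0% |

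For the shift tables, M/W runs from 1.059 (30% removed) to 1.227 (70%). A Day 1 value up to 5.9% to 22.7% above the upper limit would therefore read as within range on Day 3. M/F gives 10.5% to 31.7% on Day 5. These are widths of a band; nothing in the documents says how many of the 30 subjects would lie in it.

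**Sensitivity to the build-up assumption.** Let the level x approach a ceiling of 1 instead, so that each gap maps x to 1 − (1 − x(1 − f))·exp(−k·gap), with k = ln 2/half-time, iterated to a steady cycle:

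| Assumed half-time | 30% removed, Day 3 / Day 5 | 70% removed, Day 3 / Day 5 |
|---|---|---|
| 8 days | −5.7% / −9.1% | −17.8% / −22.2% |
| 1 day | −3.9% / −4.6% | −9.7% / −10.4% |
| 0.5 day | −1.4% / −1.5% | −3.3% / −3.4% |
| 0.25 day | −0.1% / −0.1% | −0.3% / −0.3% |

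The direction is stable, but the size runs from negligible to about a quarter, depending wholly on inputs that the documents do not supply. The model says nothing about vital signs, or about analytes that dialysis barely removes.

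**What the planned tables already give.** Sections 12.10.3 and 12.10.6 cover every visit, so the Day 8 change from baseline, and the Day 8 laboratory shift, will be produced. With Day 1 as baseline, that is the matched comparison.

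**The case for a change.** The strongest case for acting is that the remedy costs almost nothing. The SAP could name Day 1 as baseline, designate Day 8 versus Day 1 as the comparison to interpret, and mark Days 3 and 5 as short-gap. Section 12.12 promises a baseline definition but not a matched comparison, so the SAP might never say which column to trust.

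The gap arithmetic behind this stands, and so does the possibility that the SAP stays silent. The benefit does not follow, for three reasons:

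- Table 1 prints the dialysis weekday above each visit. Section 9.7 records session start and stop times, Section 9.1 the date of the last dialysis, and individual data are listed. A reader who knows dialysis patients can see the pattern and check it.
- Making Day 8 the comparison to interpret would favour the visit with the least drug on board. With assumed 4-hour sessions, single-phase decay and the half-lives in Sections 1.1 and 1.2.2.1 (24 to 49.3 h), the fraction of the last dose's concentration left is 2^(−44/24) = 28% to 2^(−44/49.3) = 54% before Days 3 and 5. Before Day 8 it is 2^(−68/24) = 14% to 2^(−68/49.3) = 38%. Each column has a strength that the other lacks, so showing all visits alike is a fair presentation.
- Day 1 as baseline is itself an assumption. It is the likely choice, but the protocol does not state it.

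**Conclusion.** No change to the plan is needed. If Day 1 is baseline and the usual weekly sessions are attended, Day 3 and Day 5 values of well-dialysed analytes carry a downward timing component. Under the assumed models it ranges from close to nothing to 18.5% on Day 3 and 24.1% on Day 5, for up to 70% removed per session. That is a caution for whoever interprets the tables. The matched Day 8 contrast is already planned, the baseline rule has a stated home in the SAP, and a designation or label would alter no estimate. Safety is a secondary objective, every analysis is descriptive, no threshold or decision rests on these tables, and no pharmacokinetic result is touched. A footnote giving the preceding gap for each visit would do no harm, but it is a matter of style.

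One clerical slip surfaced. Section 8.3.7 places the Day 8 dialysis on Friday or Saturday, whereas Table 1 gives Monday or Tuesday, which is also seven days after Day 1. The two places should be reconciled as an editorial matter. The gaps above follow Table 1.

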12.11 Other Evaluations

12.11.1 Dialysis Details

Dialysis details will be listed only using the SAF.

12.12 Handling of Missing Data

Procedures for managing missing data, imputation for missing or partially missing data will be provided in the SAP.

Definitions of baseline will be specified in the SAP and will include rules for identification of baseline values when assessments are missing at the scheduled baseline visit.

13. STUDY ETHICAL CONSIDERATIONS

13.1 Ethical Conduct of the Study

The study will be conducted according to the principles of the World Medical Association's Declaration of Helsinki [15], and the ICH guidelines for Good Clinical Practice (GCP) [16] as amended. The Sponsor will ensure that the study complies with all local, federal, or country regulatory requirements.

The Investigator must ensure the anonymity of all subjects participating in the study. Each subject will be assigned a unique subject number, and this should be used on all forms associated with the subject's documents or samples that will be supplied to the Sponsor or any party completing testing on behalf of the Sponsor (e.g., blood for central laboratory assessments).

All anonymous data remains the property of the Sponsor.

13.2 Informed Consent

The ICF used for the study must comply with the Declaration of Helsinki, regulatory and legal requirements of China, and ICH guidelines; and must have been approved by the IEC prior to use. The Investigator or an authorised associate must explain orally and in writing the nature of the study and the treatment in such a manner that the subject is aware of potential benefits and risks. Subjects must also be informed that participation is voluntary and that they may withdraw from the study at any time, without prejudice. Subjects must be provided sufficient time to consider participation, including discussion with family members prior to signing the ICF. Documentation of the discussion and the date of informed consent must be recorded in the source documentation. Subjects must give informed consent in writing. If applicable, consent from female partners (who become pregnant during the study) of male subjects will also be acquired.

13.3 Independent Ethics Committee

The protocol, any protocol amendments and consent form for the proposed clinical study and any other documents required by the local IEC must be submitted by the Investigator for review and approval to the IEC. The Investigator must also ensure that the IEC reviews the progress of the study on a regular basis and, if necessary, renews its approval of the study on an annual basis. A copy of the approval letter must be forwarded to the Sponsor before the study is implemented.

Approval by the Human Genetics Resources Administration of China will be obtained prior to study initiating for the different study sites.

